### PFIZER CONFIDENTIAL

CT24-WI-GL02-RF023.0 Non-Interventional Study Protocol Template For Secondary Data Collection Study 20-May-2021

Page 23

# 9.2. Setting

The study population consists of women in the HIRD and Sweden who are at least 50 years of age. For subjects using a vaginal estrogen or E+P HT, cohort qualification status will be assessed for the first study drug dispensing (index date) during the exposure ascertainment period (see Table 1) based on the inclusion and exclusion criteria described below. For the purpose of the primary objective, non-users of vaginal estrogen, subjects with at least one gynecological visit after age 50 and without any prior or current use of vaginal estrogens at the time of their gynecological visit (index date for non-users) will be included in this population regardless of their prior use of hormone therapy. Subjects may have multiple qualifying gynecological visits. For the purpose of the secondary objective, E+P HT new users with no prior use of hormone therapy will be included.

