### 9.1.1. Time Periods

The study period, i.e., the beginning of the baseline period to the end of the follow-up period, is 01 January 2006 (earliest available date) through 31 December 2020 (or most recent available date) in the HIRD, and 01 January 1997 (earliest available date for medical record history) through 31 December 2019 (or most recent available date) in the Swedish registers. The difference between the two data sources in end of study dates is due to the difference in the lag time for populating the HIRD and the Swedish registers.

Ascertainment of exposure and follow-up will be 01 January 2007 - 31 December 2020 (or most recent available date) in the HIRD, and 01 July 2007 - 31 December 2019 (or most recent available date) in the Swedish Registers to allow for a 12- or 24-month baseline period in the HIRD and Swedish data bases, respectively. The index date is the day of initiating a study drug or, for non-users, the date of a gynecological visit that meets all inclusion and exclusion criteria. For new users of vaginal estrogens and E+P HT, a 6-month induction period is allowed following initiation of exposure and prior to beginning follow-up to allow for induction and diagnosis of endometrial cancer (Figure 1). For non-users, follow-up and accrual of person-time starts the day after the index date. The unexposed period before a woman starts any vaginal estrogen will be included as time at risk for a non-user until they begin using one of these drugs. The unexposed time at risk (non-users) will be censored if and when they start using vaginal estrogen, E+PHT or other non-study estrogen or progestogen medications. A sensitivity analysis is included that varies the length of the induction period and includes an induction period for the non-user cohort. Table 1 summarizes the different time periods for the two data sources. Patients may differ in their follow-up dates depending on when they meet the study inclusion, exclusion, and censoring criteria.

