### **Figure 2: Study Population**

Abbreviations: E+P HT, estrogen-progestogen combination hormone therapy; HDVC, high-dose Premarin VC (HIRD only); HIRD, HealthCore Integrated Research Database; LDVE, low-dose vaginal estrogen; MDVE, moderate-dose vaginal estrogen.

Note: Bolded boxes outlined in blue indicate an exposure or comparator group.

The three vaginal estrogen exposure groups and the two comparator groups are described below and summarized in Figure 2 (for definitions of study drugs and gynecological visits, see Section 9.2 Setting and Section 9.3 Variables):

- Exposure 1: New Users of LDVE.
  - o Women who had ≥1 dispensing of an LDVE during the exposure ascertainment period with prescription daily doses ≤10 mcg estradiol or ≤0.3 mg conjugated estrogen at cohort entry and no prior dispensings of vaginal estrogen. Low-dose Premarin VC (HIRD only) is defined as 0.5 g/day dose (equal to daily average strength 0.3 mg or less conjugated estrogens. It should be noted that these women may or may not have used hormone therapy prior to the index date and will be included regardless of such prior use.
- Exposure 2: New Users of MDVE.
  - Women who had ≥1 dispensing of a MDVE during the exposure ascertainment period with prescription daily doses >10 mcg 25 mcg estradiol or >0.3 mg 0.45 mg conjugated estrogen at cohort entry and no prior dispensings of vaginal estrogen. It should be noted that these women may or may not have used hormone therapy prior to the index date and will be included regardless of such prior use. The Swedish cohort will only include subjects with ≥ 1 dispensing of 25mcg estradiol (Vagifem).
- Exposure 3: New Users of HDVC (HIRD Only).
  - Women who had ≥1 dispensing of Premarin VC during the exposure ascertainment period with prescription daily doses >0.45 mg conjugated estrogen at cohort entry and no prior dispensings of vaginal estrogen. It should be noted that these women may or may not have used hormone therapy prior to the index date and will be included regardless of such prior use.
- Primary Comparator: Non-users of vaginal estrogen.
  - Women who had  $\geq 1$  gynecological visit during the exposure ascertainment period, and no dispensings of vaginal estrogen prior to or on the gynecological visit. It should be noted that these women may or may not have used hormone therapy prior to the index date and will be included regardless of such prior use.

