### 9.3.1. Exposures, Comparators, and Treatment Episodes

GPI codes will be used to identify vaginal estrogen and E+P HT products in the HIRD, (Annex 1: Appendix B) and ATC codes, formulation, brand name, and strength will be used to identify vaginal estrogen and E+P HT Swedish products (Annex 1: Appendix F). Gynecological visits for non-users will be identified in the HIRD using ICD-9-CM and ICD-10-CM diagnostic codes, HCPCS codes for annual exams, CPT codes for pap smear procedures, and physician's specialty code (Annex 1: Appendix C). Gynecological visits will be captured as non-primary outpatient care in the Swedish NPR. Proxies for gynecological visits (i.e., related procedure codes, specialist encounters, and/or reimbursement) will be considered, as appropriate.

Treatment episodes (Annex 1: Appendix I) will be created based on segments of continuous use among the study drug treatment groups, i.e., LDVE, MDVE, HDVC, and E+P HT. Continuous use is defined as consecutive drug dispensings for a treatment group, with no more than 90 days between the end of the days' supply of the earlier prescription and the dispensing date of the next prescription. In order to determine exposure status for vaginal estrogen users during the treatment episode, daily dose must first be computed for each prescription starting with the index dispensing. In the HIRD, daily dose for vaginal estrogen dispensings will be calculated as the drug strength dispensed multiplied by the drug quantity and divided by the days' supply. In Sweden, days' supply is not directly available from the SPDR. Thus, days' supply and daily dose will be estimated for each dispensed vaginal estrogen prescription based on assumptions such as defined daily dose and duration for use. For the E+P HT comparator group, dispensed amount of drug, drug strength and defined daily dose will be used to construct treatment episodes of continuous use. Exposure definitions will be further detailed in the statistical analysis plan (SAP).

The prescription daily doses of the vaginal estrogen dispensings will then be categorized as follows:

- LDVE: <10 mcg/day estradiol or <0.3 mg/day conjugated estrogen;
- MDVE: >10 25 mcg/day estradiol or >0.3 0.45 mg/day conjugated estrogen;
- HDVC: >0.45 mg/day conjugated estrogen.

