Vaginal estrogen users will enter the exposure group corresponding to the dose of their first study drug dispensing. Women whose first dispensing was E+P HT will enter the E+P HT comparator group. If a vaginal estrogen user changes dose categories or switches to E+P HT, she will be censored on the dispensing date of the new prescription. Similarly, if an E+P HT user switches to vaginal estrogen use, she will be censored on the vaginal estrogen dispensing date.

Patients may use different products and strengths for study drugs within their treatment group. If there are overlapping prescriptions for different products within the same treatment group, then it will be assumed that the patient stopped taking the first prescription drug and started the second prescription drug on the day it was dispensed (no stockpiling). If the patient has overlapping prescriptions for the same drug and dose, the prescriptions will be stockpiled, i.e., the overlapping days from the second prescription will be added to the end of the days' supply of the first

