### 9.3.4. Baseline Covariates

The study will identify and describe baseline covariates and prior use of estrogen and progestogen use using all available data prior to and including the index date (see Section 9.1.1 Time Periods). A continuous variable measuring the duration of use will be created for each of the following drug categories:

- Single-entity progestogen contraceptives (oral, transdermal, or injectable);
- E+P contraceptives (oral, transdermal, or injectable).
- Unopposed estrogen hormone therapy: These include oral, transdermal, and injectable singleentity estrogen medications without a progestin dispensed during the baseline period.
- Unopposed progestin hormone therapy: These include oral, transdermal, injectable, and vaginal medications without an estrogen dispensing during the baseline period.
- Progestin opposed estrogen hormone therapy: These include prior use of E+P HT study drugs and subjects who used single-entity estrogen AND single-entity progestin medications during the baseline period (the two medications' usage does not need to overlap).
- Other opposed estrogen hormone therapy: These include prior use of estrogen-testosterone combination medications, conjugated estrogen-bazedoxifene, or the use of single-entity estrogen and single-entity testosterone medications during the baseline period (the two medications' usage does not need to overlap).
- No prior estrogen or progestin hormone therapy use (not including contraceptives). This will be a binary variable indicating no prior hormone therapy use.

Prior contraceptive use may be further divided into categories for time since last dispensing:

• <6 months;

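### The entry rules conflict on women who used E+P HT before vaginal estrogen: one set sends them to the E+P HT comparator group, another includes them in the exposed cohorts

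*Protocol*

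**What the plan says.** One set of rules ties entry to the first study drug:

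- Section 9.2, for users of vaginal estrogen or E+P HT: "cohort qualification status will be assessed for the first study drug dispensing (index date) during the exposure ascertainment period". Section 9.1.1 agrees: "The index date is the day of initiating a study drug or, for non-users, the date of a gynecological visit". Inclusion criteria 2 (age) and 3 (baseline) in 9.2.1 refer to the same first dispensing.
- E+P HT counts as a study drug. Section 9.3.1 builds treatment episodes from "segments of continuous use among the study drug treatment groups, i.e., LDVE, MDVE, HDVC, and E+P HT".
- Section 9.3.1 on assignment: "Women whose first dispensing was E+P HT will enter the E+P HT comparator group". On later change: "if an E+P HT user switches to vaginal estrogen use, she will be censored on the vaginal estrogen dispensing date". The protocol does not describe such a woman entering a vaginal estrogen cohort afterwards.

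A second set admits women with earlier hormone therapy to the exposed cohorts:

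- Section 9.1.2 (text under Figure 2) says of each vaginal estrogen group that the women "may or may not have used hormone therapy prior to the index date and will be included regardless of such prior use". Primary Objective 1 in Section 8 has the same scope.
- Section 9.2.2 lists the prior E+P HT exclusion for vaginal estrogen users under the secondary analyses only.
- Section 9.3.4 defines the progestin-opposed category of prior use: "These include prior use of E+P HT study drugs and subjects who used single-entity estrogen AND single-entity progestin medications". Section 9.7.3.1 makes this category a subgroup of the primary comparison.

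Non-users are indexed at a gynecological visit (9.1.2, 9.2). Prior vaginal estrogen bars them; prior E+P HT does not.

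**The concern.** Both sets of rules cannot be programmed for the same woman. If the first-study-drug rule is followed, an in-window E+P HT history keeps a woman out of the exposed cohorts but not out of the non-user cohort. Primary Objective 1 would then not cover vaginal estrogen new users whatever their hormone history. In Primary Objective 2, the E+P part of the progestin-opposed stratum would have comparators and very few exposed women.

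Two organisations build the cohorts separately, one in the HIRD and one in Sweden, and the hazard ratios are then pooled (9.7.5). If each read the rule differently, the pooled estimate would combine different populations.

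**Working it through.** **1. Follow one woman through each set of rules.** Suppose E+P HT is first dispensed in 2010 and LDVE in 2015, with no earlier vaginal estrogen and age over 50 throughout.

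- Under 9.2 and 9.3.1, her first study-drug dispensing is E+P HT in 2010. She enters the E+P HT group, is censored in 2015, and is never an LDVE new user.
- Under 9.1.2, 9.2.2 and 9.3.4, she has an LDVE dispensing in the window and no earlier vaginal estrogen. She is an LDVE new user from 2015, in the progestin-opposed stratum.
- With a gynecological visit in 2014 she also qualifies as a non-user, since only vaginal estrogen bars entry there.

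Two variants under the literal rule: if the E+P HT dispensing came at age 48, she fails criterion 2. If she had used another hormone therapy before E+P HT, the secondary exclusions also keep her out of the E+P HT group, so she enters no drug cohort.

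**2. Who with prior E+P HT could still be exposed under the literal rule?** Only women whose E+P HT was dispensed solely before the window. Inputs: Table 1 (windows), 9.4.1 (HIRD claims from 01 January 2006), 9.4.2 (drug register from July 2005).

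| Source | Ascertainment window | Observable E+P HT before it |
|---|---|---|
| HIRD | 01 Jan 2007 to 31 Dec 2020 (14.0 years) | 2006 (1 year) |
| Sweden | 01 Jul 2007 to 31 Dec 2019 (12.5 years) | Jul 2005 to Jun 2007 (2 years) |

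A woman first observed after the window opens can have no such history.

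**3. Is power affected?** First, the plan's own HIRD figure (9.5.1). By Schoenfeld's formula with two-sided alpha 0.05 (sidedness is not stated), 80% power, hazard ratio 1.5 and a 1:4 ratio:

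- Events = (1.960 + 0.842)² / (0.2 × 0.8 × ln(1.5)²) = 298.4, rounded up to 299. The plan has 60 + 239 = 299.
- Exposed: 298.4 × 0.2 / 0.000745 = 80,104 person-years; divided by 2.4 = 33,377 women (plan: 33,377).
- Comparators: 298.4 × 0.8 / 0.000745 = 320,416 person-years; divided by 2.4 = 133,507 women (plan: 133,504).

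The plan's figure is reproduced. Now remove an assumed share of the 152,941 HIRD LDVE users, keep the 1:4 ratio, and apply the background rate to both groups as the plan does:

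| Assumed loss | Exposed women | Power at hazard ratio 1.5 |
|---|---|---|
| 10% | 137,647 | 99.99% |
| 30% | 107,059 | 99.9% |
| 50% | 76,471 | 98.9% |

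The 50% row: 76,470.5 × 2.4 × 0.000745 × 5 = 684 events. The losses are assumptions; the protocol gives no share.

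**4. Annex 3.** The Swedish LDVE estimate falls from 255,895 to 132,373 after an allowance for excluding women who use E+P HT, non-study estrogen or non-study progestogen: 1 − 132,373 / 255,895 = 48.3%. Sizing the cohort after excluding E+P HT users does not fit the inclusive definition in 9.1.2.

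**The case against.** The strongest reply is that the protocol's intent is clear. The objectives, group definitions, exclusion list and subgroup plan all admit prior E+P HT users. If the first-study-drug rule already kept them out, the exclusion in 9.2.2 would have almost nothing left to do. The first study-drug dispensing can be read as the first dispensing of the drug that defines the cohort, and nowhere is a woman expressly limited to one index date or one cohort. On that reading the age-48 case also disappears. Section 9.3.1 adds that the SAP will detail exposure definitions.

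Much of this stands. A reader might infer that prior E+P HT users simply cannot enter the exposed cohorts. The documents do not support that as a settled rule, because several sections state the reverse, and even the literal rule admits women whose E+P HT all came before the window. But the within-class reading is never stated, and the assignment sentence in 9.3.1 works across classes, by which drug came first. Deferring detail to the SAP does not say which of two conflicting protocol rules prevails.

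A reader might also take the 48.3% from Annex 3 as the share affected, or as a bound on it. It is neither. It is a Swedish feasibility figure from aggregate data, mixes E+P HT with other hormones, and takes no account of which drug came first.

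**Conclusion.** The entry rules contradict each other and need reconciling before cohorts are built. The consequence depends on the literal rule in 9.2 and 9.3.1 being the one programmed. In that case women with in-window E+P HT before vaginal estrogen are missing from the exposed cohorts but present among non-users. Observable prior E+P HT in the exposed then comes from one pre-window year in the HIRD and two in Sweden.

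The effect falls on the target population of Primary Objective 1 and on the E+P part of the progestin-opposed stratum of Primary Objective 2. The rest of that stratum, women who used single-entity estrogen and single-entity progestin, is not touched by this rule, and the subgroup analysis is in any case conditional on sample size.

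A reader might infer that the overall hazard ratio is biased. That is not shown. Section 9.7.1 lists duration of prior hormone therapy among the variables considered for the propensity score; if it is used, matching may drop non-users with an E+P HT history, which narrows the population without necessarily distorting the comparison. Power at hazard ratio 1.5 stays at 98.9% or more in the HIRD for assumed losses of up to half the exposed women.

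**What to change.** In 9.2, inclusion criterion 2 of 9.2.1, and 9.3.1, define the index date separately for each comparison:

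- Primary exposed cohorts: the first vaginal estrogen dispensing in the ascertainment window, whatever E+P HT came before it.
- Secondary cohorts: the first study-drug dispensing in women with no prior hormone therapy.

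State that a woman may contribute to more than one cohort over time; in particular, one censored from the E+P HT group at vaginal estrogen may enter the corresponding primary exposed cohort from that date. Then bring 9.1.2, 9.2.1, 9.2.2, 9.3.1, 9.3.4 and the LDVE sizing step in Annex 3 into line.

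The cost is protocol wording and cohort-building code, with no new data. A woman may appear in both a primary and a secondary cohort, but these are analysed separately.

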# 9.2.1. Inclusion Criteria

Patients must meet all of the following inclusion criteria to be eligible for inclusion in the study:

1. Women must have  $\geq 1$  study drug dispensing, or  $\geq 1$  gynecological visit, that meets each of the following criteria to be eligible for inclusion in a study cohort (Figure 3; for additional details on study drugs and gynecological visits, see Section 9.3 Variables):

• ≥1 dispensing of vaginal estrogen not indicated for severe vasomotor symptoms or any E+P HT, or a gynecological visit for non-users, from 01 January 2007 through 31 December 2020 (or most recent available date) in the HIRD, and 01 July 2007 – 31 December 2019 (or most recent available date) in Sweden (see Annex 1: Appendix B and Appendix F for vaginal estrogen and E+P HT medications)

Vaginal estrogen: Vaginal estrogen drugs include products which are approved only for one or more symptoms of vulvar and vaginal atrophy due to menopause. Thus, Femring (estradiol acetate vaginal) and Ogen (estropipate vaginal) which are also indicated for moderate to severe vasomotor symptoms, are not included as study drugs. Estrace (estradiol cream) is also excluded due to its indication for vasomotor symptoms and its high concentration of estradiol resulting in greater systemic absorption. Vaginal estrogen study drugs include the following products:

HIRD: Estring, Vagifem, Yuvafem, Imvexxy, generic estradiol (tablet), and Premarin VC;

Sweden: Oestring and Vagifem.

E+P HT: oral, transdermal, or injectable estrogen-progestogen combination hormone therapy products.

Gynecological visit: outpatient office visit with provider specialty of gynecology, or diagnosis/procedural codes for gynecological exam or Pap smear.

2. Female aged  $\geq$ 50 years on the first study drug dispensing date or on the gynecological visit date for non-users (the index date).

3. Minimum required baseline observation period:

#### PFIZER CONFIDENTIAL

[figure not shown]
HIRD: A minimum of 12 months of continuous eligibility in the HIRD prior to and including the study drug dispensing date, or the gynecological visit date for non-users.

Sweden: A minimum of 24 months of medical history (i.e., 24 months of continuous residence in Sweden with no migration observed) prior to and including the study drug dispensing date, or the gynecological visit date for non-users.

The reason for using different baseline requirements is that greater turnover in the HIRD reduces the duration of enrollment, and one wishes to preserve available enrollment for follow-up. The baseline period includes all available enrollment data (HIRD) and medical history (HIRD, Sweden) on and prior to the index date (date of first dispensing of a study drug or gynecological visit).

4. Must be enrolled (HIRD) or residing in Sweden (Swedish registers) on the day after the index date.

#### Figure 3. Cohort Selection for Primary Study Population: Vaginal Estrogen Treatment Groups and Non-Users

#### Abbreviations: HIRD, HealthCore Integrated Research Database

Vaginal estrogens include vaginal estradiol estrogen (excluding Estrace), and vaginal conjugated estrogen (Premarin Vaginal Cream, HIRD only) in low, moderate, and high doses.

Censoring date for new users is earliest of: hysterectomy, endometrial cancer, switching of treatment group study drug, dispensing of an estrogen-containing product (vaginal or non-vaginal) that does not belong to a treatment group, dispensing of a progestogen-containing product (vaginal or non-vaginal), death, disenrollment (HIRD), emigration from Sweden (Sweden), end of the study period. Censoring date for non-users is earliest of: hysterectomy, endometrial cancer, dispensing of any study drug, dispensing of an estrogen-containing product (single-entity or combination, vaginal or non-vaginal) that does not belong to a treatment group, dispensing of a progestogen-containing product (single-entity or combination, vaginal or non-vaginal), death, disenrollment (HIRD), emigration from Sweden (Sweden), end of the study period. (Sweden), end of the study period.

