### 9.2.3. Post-Index Period

For new users of vaginal estrogen and E+P HT, the post-index period includes the induction period and the follow-up period. The induction period starts the day after the index date and lasts for six months or until the one of the censoring criteria (below) is met. If a censoring criterion has been met during the induction period, that subject is censored and contributes no follow-up time in the main analysis but may be included in a sensitivity analysis (see Section 9.7.4 Sensitivity Analyses). If no censoring criteria has been met during the six-month induction period, the follow-up period begins on the day after the end of the induction period. Person-time for new users of vaginal estrogen and E+P HT will only be counted during follow-up and only endometrial cancer cases occurring during follow-up will be included in the analysis as cases.

The endometrial cancer incidence rate in non-users is unrelated to treatment so the induction period does not apply to this group. Therefore, follow-up and person-time accrual for non-users begins the

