### PFIZER CONFIDENTIAL

day after their index date (i.e., the date of a gynecological visit that meets all inclusion and exclusion criteria). Follow-up for all subjects will extend through the earliest of the following censoring events:

- Hysterectomy;
- Endometrial cancer;
- Dispensing of an estrogen hormone therapy product not included as a study drug (single-entity or combination, vaginal or non-vaginal formulation)
- Dispensing of a progestogen hormone therapy product not included as E+P HT (single-entity or combination, vaginal or non-vaginal formulation);
- End of continuous health plan eligibility (HIRD only);
- Emigration from Sweden (Sweden only);
- Death;
- End of the study period.
- Dispensing of a study drug that is in a different treatment group than the index treatment group, i.e., switching between LDVE, MDVE, HDVC, or E+P HT treatment groups;

Additional censoring criteria for non-users only:

• Dispensing of any study drug, which are defined in Section 9.2.1 Inclusion Criteria.

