# 9.7.4. Sensitivity Analyses

Several sensitivity analyses will be conducted. Results from analyses conducted in the HIRD and Sweden will be pooled.

- HIRD and Sweden: The impact of various induction periods on the HR estimates will be assessed by calculating IRs and HRs for LDVE users and nonusers using no induction period, and an induction period of 3 months (lagging the start of follow-up for the LDVE group), and 12 months (Annex 1: Table 7 and 12). Additionally, the impact of lagging the start of follow-up for the non-user group will be assessed. LDVE users will be compared to nonusers with a six-month induction period for both groups.
- 2. HIRD and Sweden: To evaluate the possibility of informed censoring and selection in the main analysis resulting from the inclusion of multiple treatment episodes, a sensitivity analysis restricting follow-up to the first treatment episode will be conducted (Annex 1: Table 8 and 12). The HR of endometrial cancer will be calculated implementing censoring upon restart of index drug. The rationale is that the decision about whether or not to restart treatment could be influenced by past treatment experience. The comparison will be done for the following cohorts:
  - a. LDVE users versus non-users.
  - b. MDVE users versus non-users.
  - c. HDVC users versus non-users (HIRD only).
  - d. LDVE new users versus E+P HT new users.
  - e. MDVE new users versus E+P HT new users.
  - f. HDVC new users versus E+P HT new users (HIRD only).
- 3. HIRD and Sweden: An intent-to-treat (ITT) analysis will be conducted for the possibility of informed censoring and selection in the main analysis resulting from censoring on switching treatment. The ITT analysis will consider patients at risk during the entirety of their follow-up, regardless of discontinuing, or switching treatment, until the earliest of a diagnosis of endometrial cancer, a hysterectomy procedure, health plan disenrollment (HIRD only), emigration (Sweden only), death, or end of study. The HRs will be calculated comparing LDVE users to non-users, and, if sample sizes allow, stratified by prior use of hormone therapy. (Annex 1: Table 8 and 12).

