# 4. ENDOMETRIAL CANCER CASE IDENTIFICATION

#### 4.1. Claims-Based Identification of Potential Endometrial Cancer Cases

Potential cases of endometrial cancer in the current study will be identified via a screening algorithm in each exposure and comparator cohort, i.e., LDVE, MDVE, HDVC, E+P HT, and non-users, using ICD-9 and ICD-10 codes. The screening algorithm will be defined as at least one ICD-9-CM or ICD-10-CM diagnosis code listed in Table 1 in any position (primary, secondary, etc.) and any location (outpatient, inpatient, ED, etc.) during the follow-up period. This algorithm was informed using preliminary case counts of patients in the HIRD with codes beginning with 182 and C54. Endometrial cancer is the most common cancer with codes starting with 182 or C54 and the vast majority of patients had either the code 182.0 or C54.1. The codes 182.8, C54.8 and C54.9 were also included to improve the capture of all possible cases of EC. Therefore, with this screening algorithm, an assumption is that all possible cases of EC have been captured. The index date of diagnosis will be the date of the first encounter with a diagnosis code in Table 1. Cases diagnosed during baseline will be considered prevalent cases and excluded from analysis.

	ICD-9-CM		ICD 10-CM
Code	Description	Code	Description
182.0	Corpus uteri, except isthmus [Endometrium] [Myometrium] [Fundus] [Cornu]	C54.1	Malignant neoplasm of endometrium
182.8	Other specified sites of body of uterus [Malignant neoplasm of contiguous or overlapping sites of body of uterus whose point of origin cannot be determined]	C54.8	Malignant neoplasm of overlapping sites of corpus uteri
N/A	N/A	C54.9	Malignant neoplasm of corpus uteri, unspecified

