#### 6.2. Clinical Criteria for Endpoint Adjudication

The clinical criteria for adjudicating EC events identified in claims includes the presence of the following in the medical record:

1. Documentation of an EC diagnosis (any stage) by a treating healthcare provider.

AND

2. Positive results from an endometrial biopsy, pathology report, or surgical procedure, OR treatment with medications consistent with EC care.

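### Follow-up stops at hysterectomy with no window after it, so an endometrial cancer first recorded after the operation date is censored and not counted

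*Protocol*

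**What the plan says.** Four parts of the protocol together decide which cancers count.

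- **Censoring.** Section 9.2.1, Figure 3 footnote 2, states for the exposed groups "Censoring date for new users is earliest of: hysterectomy, endometrial cancer, switching of treatment group study drug" and for the comparator "Censoring date for non-users is earliest of: hysterectomy, endometrial cancer, dispensing of any study drug". Section 9.2.3 repeats the list for everyone: "Follow-up for all subjects will extend through the earliest of the following censoring events". Hysterectomy and endometrial cancer are separate entries in it. Neither place gives a window after hysterectomy or says which entry prevails on a shared date.
- **Case definition.** For new users, Section 9.2.3 says that "only endometrial cancer cases occurring during follow-up will be included in the analysis as cases". Section 9.7.2 computes every incidence rate from events within follow-up. For the HIRD, Annex 2 section 4.1 requires a qualifying code in any position and "any location (outpatient, inpatient, ED, etc.) during the follow-up period". It dates the event as follows: "The index date of diagnosis will be the date of the first encounter with a diagnosis code in Table 1".
- **Intent-to-treat analysis.** Section 9.7.4 item 3 drops censoring on switching but still follows women "until the earliest of a diagnosis of endometrial cancer, a hysterectomy procedure, health plan disenrollment (HIRD only" and the remaining stops.
- **Evidence for a case.** Annex 2 section 6.2 requires a documented diagnosis together with supporting evidence, which may be "Positive results from an endometrial biopsy, pathology report, or surgical procedure" or cancer-directed medication.

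**The concern.** Hysterectomy is a sensible end to time at risk, since no new endometrial cancer can arise afterwards. It is not a sensible end to case finding. The removed uterus goes to pathology, and a cancer found there was present at the operation but may be first coded or registered some days later. Under the stated rules that woman leaves the risk set as cancer-free on the day her disease was removed.

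The primary objectives are to estimate as well as to compare incidence rates, so lost events matter even when the loss is equal across groups. If the loss differs by group, the hazard ratio moves too, in a safety study whose purpose is to detect or exclude a raised risk.

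**Working it through.** **1. Does any rule or analysis catch these cases?** Take a woman with a hysterectomy on day H and a first cancer record on a later day.

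- Main analysis: the earliest listed event is the hysterectomy, follow-up ends on day H, and the cancer record lies outside it. Not counted.
- Intent-to-treat (9.7.4 item 3): same stop, same result.
- Quantitative bias analysis (9.7.4 item 9): concerns hysterectomies and hormone use missed before the index date, not cancers recorded after a captured hysterectomy.
- Validation: Annex 2 section 4.2 samples only women who meet the screening rule during follow-up. Section 7.1 defines PPV as true positives over true plus false positives. A PPV from that sample cannot reveal missed cases, and the correction in section 7.2 cannot restore them.

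If the first cancer record falls on day H, hysterectomy and cancer tie as earliest event and no passage settles the tie. If it falls before day H, the case counts.

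**2. Reproducing the plan's event figure.** Inputs from Section 9.5: HR 1.5, α = 0.05 (taken as two-sided), 80% power, 1:4 matching (exposed share 0.20). Schoenfeld's formula:

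d = (1.960 + 0.842)² / [0.20 × 0.80 × (ln 1.5)²] = 7.849 / 0.02630 = 298.4, so 299 events.

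This matches the stated 60 + 239 in the HIRD and 299 in Sweden. The sample-size figures are not at fault here.

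**3. Events and rates at stake.** HIRD inputs (9.5.1): 152,941 LDVE new users, 2.4 years, 74.5 per 100,000 person-years.

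Expected LDVE events at the background rate = 152,941 × 2.4 × 74.5/100,000 = 273.

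Let s be the share of cancers first recorded after the hysterectomy date. The protocol does not give s; 5 to 20% is an assumption.

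| s | LDVE events lost (273 × s) | Background rate observed, 74.5 × (1 − s) |
|---|---|---|
| 5% | 14 | 70.8 |
| 10% | 27 | 67.1 |
| 20% | 55 | 59.6 |

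**4. Hazard ratio.** With shares s₁ in users and s₀ in non-users, observed HR = true HR × (1 − s₁)/(1 − s₀).

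| s₁ | s₀ | Factor | True 1.5 seen as | True 1.0 seen as |
|---|---|---|---|---|
| 10% | 10% | 1.00 | 1.50 | 1.00 |
| 20% | 10% | 0.80/0.90 = 0.89 | 1.33 | 0.89 |
| 10% | 20% | 0.90/0.80 = 1.13 | 1.69 | 1.13 |

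**5. Power with equal loss.** Both groups together, at the background rate: HIRD 5 × 273.46 = 1,367 events; Sweden 5 × 100,800 × 2.4 × 70.4/100,000 = 852 events. Even with 30% lost, power for HR 1.5 is 99.9% in the HIRD (957 events) and 97.7% in Sweden (596 events).

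**The case against.** The case against is strong on several extensions that a reader might infer.

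- **Cancers recorded on the day of surgery are lost.** Not established. Section 9.2.3 carries follow-up through the earliest event, and endometrial cancer is itself on the list. A single code on the surgical encounter could qualify under Annex 2 section 4.1. The gap is the missing tie rule, which the SAP, not available here, could supply.
- **A rule of two or more encounters would also drop cancers coded before surgery.** This depends on an algorithm not yet chosen. Screening needs one code, and Annex 2 section 7.2 aims to maximize detection. No passage says that a second code must precede censoring.
- **Annex 2 section 6.2 shows that cancers are first found at surgery.** It shows only that surgical evidence can confirm a case. A cancer coded after biopsy and confirmed on the specimen meets the criterion and counts.
- **The hazard ratio is pushed toward or below 1.** The rationale in Section 7 makes a larger loss in exposed women conceivable, but the protocol has no data on this, and the opposite imbalance inflates the ratio.
- **Sweden suffers to the same extent.** Cases there come from the Cancer Register, and the protocol does not say which register date is used. The earliest-event rule applies, but the frequency of post-surgical dating is unknown.

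It is also fair that the size rests wholly on assumed shares, and that 273 uses a median follow-up as if it were a mean. None of this answers the core point: a first record dated strictly after the hysterectomy is excluded by the stated rules. Nor is this only an SAP detail. The protocol itself fixes both the censoring list and the case rule, and Section 9.7 ties major changes to primary endpoint definitions to a protocol amendment.

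**Conclusion.** The point holds for cancers first recorded after the hysterectomy date. They are censored as cancer-free in the main and intent-to-treat analyses, and no listed sensitivity, bias or validation work recovers them. The same-day case is unresolved rather than wrong.

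Incidence rates are understated in proportion to the share so recorded. An assumed 5 to 20% corresponds to 14 to 55 of about 273 HIRD LDVE events. That count assumes the background rate, 2.4 years as average follow-up and the full estimated cohort. Equal shares leave the hazard ratio unchanged. Shares of 20% and 10% shift it by a factor of 0.89 or 1.13, depending on which group loses more, and the documents do not support choosing a direction. This is a question of bias, not of power.

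**What to change.** - In Section 9.2.3, the Figure 3 footnote and Section 9.7.4 item 3, state that an endometrial cancer recorded on the hysterectomy date, or within a fixed window after it (for example 90 days), is an event dated at the hysterectomy. State that the event takes precedence over censoring on the same date. Person-time is unchanged.
- Extend the screening in Annex 2 section 4.1 and the sampling in section 4.2 to the same window. Otherwise the PPV used to correct the main estimates would not cover these codes.
- Apply the rule in both data sources, using the register diagnosis date in Sweden.
- Add a sensitivity analysis that varies the window, including same-day only, because 90 days is a working choice and not a figure from the protocol.

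The cost is small. The study is retrospective, so the records already exist; three passages need a sentence each and Annex 2 a short edit. The downside is that a few miscoded post-surgical claims may enter in the HIRD, which the extended validation sample would measure.
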